3.2 Exclusion Criteria

1. Prior history or current diagnosis of leukemia.
2. Have received any gene therapy products or oncolytic viral therapy.
3. Receiving allopurinol.
4. Received an investigational drug within 30 days prior to first injection of Ad/PNP.
5. Received radiation treatment < 4 weeks prior to first injection of Ad/PNP and does not have any RECIST 1.1 evaluable lesions that are outside the radiation field. (If the patient has RECIST 1.1 evaluable lesions outside the radiation field then they can be included.)
6. Received chemotherapy (systemic anticancer treatment) < 4 weeks prior to first injection of Ad/PNP and have not recovered from all the related side effects. (If the patient has recovered from all related side effects or has reached a new baseline, then they may begin receiving treatment at **sooner** than 4 weeks).
7. Have significant baseline neuropathy ($>$ Grade 2 based on Common Terminology Criteria for Adverse Events [CTCAE] v5.0)
8. Uncontrolled intercurrent disease (e.g., diabetes, hypertension, thyroid disease, active infection)

9. Had within 6 months prior to enrollment: myocardial infarction (MI), cerebral vascular accident (CVA), uncontrolled congestive heart failure (CHF), significant liver disease, unstable angina.
10. Fever (temperature $> 38.1^{\circ}\text{C}$ orally).
11. Receiving chronic systemic corticosteroids (> 3 weeks) or any chronic immunosuppressive medications within 14 days prior to first injection of Ad/PNP. Subjects receiving short courses of corticosteroids are considered eligible for the study.
12. Receiving anticoagulants other than those to maintain patency of venous lines.
13. Women who are pregnant or breast feeding.
14. History of human immunodeficiency virus (HIV) infection. No requirement for testing.

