4.2 Administration of Ad/PNP-F-araAMP per Cycle

With each cycle, subjects will receive 3 intratumoral administrations of 2.0×10^{11} VP Ad/PNP over 2 days followed by 3 daily infusions of 25 mg/m^2 F-araAMP in the outpatient clinic or in-hospital at the discretion of the investigator. The physician or a designee trained to do the injections by the Principal Investigator (PI) will administer intratumoral Ad/PNP during each cycle. The outpatient unit is staffed with medical personnel to treat emergency and non-emergency medical events.

Ad/PNP will be given via direct intratumoral injection three times over 2 days. If needed, the investigator may utilize radiologic guidance (e.g., ultrasound) to assist in the injection of Ad/PNP. Two intratumoral administrations will be given on Day 1 and one intratumoral administration on Day 2. The first administration will occur on the morning of Day 1 and the subject monitored closely for 1 hour for acute injection-related events. Approximately 3-6 hours after the first administration, the subject will receive the second intratumoral administration on Day 1. The third intratumoral administration will be given on the morning of Day 2.

Vials of Ad/PNP will be thawed and prepared for injection by the investigational pharmacy according to the Preparation of Investigational Product Instructions. In the Phase 1 study, Ad/PNP was administered intratumorally in a 0.5 ml volume ($\sim 2 \times 10^{11}$ VP/ml or $\sim 2 \times 10^{12}$ VP/ml); both dose levels showed activity and were well tolerated. In the Phase 1/2 study, 2×10^{11} VP will be administered in volumes up to 5 ml (4×10^{10} VP/ml) so that vector can be dispersed more effectively throughout needle-assessable tumor tissue.

The volume of vector injected into each tumor will be according to tumor volume. All measurable tumors that are accessible for intratumoral injection will be identified and treated for each enrolled subject

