10.3.5 Response Review

The study is designed primarily to evaluate safety with repeat treatment cycles, although the anti-tumor effect of Ad/PNP-F-araAMP will be assessed. For this study, response will focus primarily on the injected tumor(s) as the target lesion(s). Any observed effect on non-injected tumors and overall tumor response will also be assessed and recorded. Efficacy response results for injected tumors, non-injected tumors, and overall will be reported separately. Although we will evaluate response of the total tumor burden, only the injected mass will be used to primarily define efficacy. Because there is a possibility of immune-mediated anti-tumor benefit, we will also evaluate total tumor burden.

Response (CR, PR, SD, PD) is based on RECIST v1.1 (<http://www.ctep.info.nih.gov> v1.1). [6]

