### 3 STUDY DESIGN

#### 3.1 General Description

This multi-center, open-label, phase 1/2, single-arm trial will evaluate the safety and anti-tumor activity of Ad/PNP-F-araAMP in participants with recurrent cancer of the head and neck region who have relapsed following curative treatment and without additional potentially curative treatment options. The study is designed to evaluate repeat administration (up to 5 cycles) of a single dose level of Ad/PNP administered intratumorally followed by intravenous (IV) F-araAMP. This study is to be conducted at Stanford University, Emory University, and Thomas Jefferson University.

Ad/PNP will be injected intratumorally twice on Day 1 and once on Day 2 followed by 25 mg/m^2 per infusion F-araAMP daily on Days 3, 4, and 5 infused over approximately 30 minutes. The 25 mg/m^2 F-araAMP dose level is the same as that evaluated in the two highest cohorts in the Phase 1 study. Each enrolled study participant shall receive 0.5 ml/dose of Ad/PNP, to which an amount of diluent will be added based on the volume of tumors selected for treatment. The dilution of study agent is described in protocol section 4.2 and shall not exceed 5 ml regardless of the number of tumors accessible for injection.

Tumor measurements taken on Day 1 of each cycle should be used to calculate dosing for Day 1 and Day 2 of that cycle.

Participants will receive repeat administration of Ad/PNP-F-araAMP every 4 weeks (i.e., each cycle) for 5 cycles or until injected tumor progresses, unacceptable toxicity occurs, no tumor is present for injection, or participant death.

Tumor selection and classification of target vs non-target should be performed according to RECIST 1.1. Target tumors should be selected for treatment at the participant's initial treatment visit. Following the participant's initial treatment, no additional tumors should be identified as target or selected for treatment.

[figure not shown]
The same tumors should be treated at each administration of study agent. It is possible for target tumors to be identified but not treated. Non-target tumors should not be treated with study agent.

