### 6.2.2 Secondary Efficacy Endpoints and Analyses

Secondary efficacy endpoints involving response, including progression, will be assessed 2 distinct ways:

- For injected tumors (per the criteria specified in protocol section 9.3.4), and
- Overall as determined per RECIST v1.1 (<http://www.ctep.info.nih.gov>).

Efficacy responses assessments for injected tumors should be performed using the (RECIST-like) assessment according to the criteria established in section 9.3.4 (Tumor Response) of the protocol (CR, PR, PD, SD). Per the protocol, this response for injected tumors is the primary focus for response, with the efficacy endpoint of primary focus being ORR for injected tumors.

Overall efficacy response assessments should be performed per RECIST 1.1 for target and non-target tumors without consideration for which tumors were treated with the study agent. Per the protocol, this overall response per RECIST 1.1 is not the primary focus for response. Total tumor burden is also being evaluated because there is a possibility of immune-mediated anti-tumor benefit.

RECIST and protocol established response evaluation criteria should be performed/evaluated in combination with CT scan/MRI at the timepoints specified in the protocol (Visit 7 of the first,

second (if PD after first cycle), third, and last cycle. Participants with CR, PR, or SD in the injected tumor at Day 14 of the fifth or last cycle will have imaging on Day 56).

To emphasize:

- Injected tumors will not be assessed per RECIST v1.1 but solely per the criteria (from protocol section 9.3.4) which are specified below.
- Many of the endpoints differ for injected tumors vs. overall as determined per RECIST v.1.1 due to differences in their underlying component definitions of CR, PR, and PD.
- All efficacy endpoints are secondary.

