### **Injected Tumor Response Criteria Details**

The following criteria will be used to define response in injected tumors:

- Complete Response (CR): Disappearance of the injected tumor(s).
- Partial Response (PR): At least a 30% decrease in the longest diameter (LD) of the injected tumor(s), taking as reference the smallest LD.
- Progression (PD): At least a 20% increase in the LD of the injected lesion(s), taking as reference the smallest LD recorded on study (this includes the baseline LD if that is the smallest on study). Note: appearance of one or more new lesions will be considered progression in assessing overall tumor response.
- Stable disease (SD): Neither sufficient shrinkage to qualify for PR nor sufficient increase to qualify for PD taking as reference the smallest LD while on study.

Regarding injected tumors, only tumors identified as target per RECIST 1.1 at the initial study visit should be treated with the study agent (AdPNP). It is possible, based on the size(s) and location(s) of the target tumor(s), that not all target tumors will be treated with the study agent. At each administration, investigators should treat only the same tumor(s) based on those target tumors treated at the initial treatment visit. No other target tumors should be treated with the study agent at any subsequent visit. Non-target tumors should not be treated with the study agent. Response for injected lesions is assessed by the investigator and recorded in the eCRF.

Regarding non-injected tumors, the protocol does not define response assessment criteria for these tumors. Therefore, efficacy response for non-injected tumors will be taken into consideration only as an input to the RECIST 1.1 response assessment. No formal criteria-based response assessment will be performed or analyzed for non-target tumors alone. Any observable effect on non-injected tumors may be recorded by investigators in the study database.

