##### **Objective Response Rate**

Separately for injected tumors and overall (per RECIST v1.1), the objective response rate (ORR) is defined as the number of participants who exhibit a BOR response of CR or PR during the up to 5 cycles of treatment divided by the number of participants in the efficacy evaluable population.

Separately for injected tumors and overall (per RECIST v1.1), the ORR will be presented; corresponding two-sided 95% Clopper-Pearson exact confidence intervals (CIs) and the underlying number of participants will also be provided. The efficacy analysis of primary focus will be the analysis of ORR for injected tumors.

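### The radiation-field condition in exclusion 5 is not carried into response assessment, so a recently irradiated injected lesion can count toward injected-tumor ORR

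*Protocol*

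**What the plan says.** **Eligibility.** Protocol Section 3.2, criterion 5, excludes a patient who had radiation less than 4 weeks before first injection and who "does not have any RECIST 1.1 evaluable lesions that are outside the radiation field". The parenthesis that follows states the exception: "If the patient has RECIST 1.1 evaluable lesions outside the radiation field then they can be included". The synopsis and the Appendix A checklist agree. Nothing requires the out-of-field lesion to be injectable, injected or used for response. Inclusion criterion 5 admits patients with further tumors that cannot be injected, on condition that the metastatic disease has no other treatment option and that local treatment may help.

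**Which tumors are injected.** Protocol Section 4.2: "All measurable tumors that are accessible for intratumoral injection will be identified and treated for each enrolled subject". The SAP is narrower. Section 3.1 says "Tumor selection and classification of target vs non-target should be performed according to RECIST 1.1", and the Injected Tumor Response Criteria Details restrict treatment to target tumors chosen at the initial visit. No radiation condition is written in either document.

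**Which tumors define response.** Protocol Section 10.3.5 says that "only the injected mass will be used to primarily define efficacy". Protocol Section 9.3.4 and the matching SAP text define response by the longest diameter of the injected tumor(s). SAP Section 6.2.2.1 states: "The efficacy analysis of primary focus will be the analysis of ORR for injected tumors". Best overall response disregards assessments made after new anticancer treatment starts, and it needs no confirmation. Radiation given before dosing is not addressed.

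**Decision criterion.** Protocol Section 12.1 and SAP Section 3.3 take 3 or more responses in 10 evaluable subjects as enough to justify further study.

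**The concern.** By tying the exception to lesions outside the field, criterion 5 implies that a lesion irradiated within 4 weeks is not enough by itself. The response rules do not follow that reasoning down to the lesion. A patient can enter because of one lesion and be scored on another that is still responding to radiation. If the qualifying lesion is among the additional tumors that cannot be injected, the injected-tumor result rests wholly on irradiated tissue.

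The trial has one arm, so radiation shrinkage cannot be separated from drug effect, and the error in ORR favors efficacy. Other features add to the exposure:

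- The first on-study scan is at Day 14 ± 2 of cycle 1, about 6 weeks or less after such radiation.
- A single unconfirmed reading is enough to make a responder.
- Screening imaging may be done from Day -30, and no text requires it to follow the radiation.
- Prior radiation is summarized only as Yes/No (SAP Section 6.1.3) and no subgroup analysis is planned (SAP Section 6.4), so the planned tables would not show the problem.

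**Working it through.** **Inputs from the documents** (Protocol Section 12.1, SAP Section 3.3): n = 10, null ORR 10%, alternative 40%, criterion 3 or more responders, one-sided exact binomial test, target alpha 10%, stated alpha 7%, stated power 83%.

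**Inputs that are assumptions:** k, the number of the 10 whose injected lesion was recently irradiated (1 or 2); and q, the chance that radiation alone produces a response (20% to 50%). The documents give neither.

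**Step 1. Reproduce the stated figures.**
- Alpha = 1 − 0.9^10 − 10(0.1)(0.9^9) − 45(0.01)(0.9^8) = 1 − 0.3487 − 0.3874 − 0.1937 = 0.0702.
- Power = 1 − 0.6^10 − 10(0.4)(0.6^9) − 45(0.16)(0.6^8) = 1 − 0.0060 − 0.0403 − 0.1209 = 0.8327.

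Both agree with the plan.

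**Step 2. Response chance of an affected patient at the null.** If radiation and drug act independently, p = 1 − 0.9(1 − q). So q = 0.2 gives p = 0.28, and q = 0.5 gives p = 0.55.

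**Step 3. One affected patient.** For the other nine at 10%, P(≥2 of 9) = 0.2252 and P(≥3 of 9) = 0.0530. The chance of meeting the criterion is p × 0.2252 + (1 − p) × 0.0530.
- p = 0.28: 0.0630 + 0.0381 = 0.101.
- p = 0.55: 0.1238 + 0.0238 = 0.148.

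**Step 4. Two affected patients.** For the other eight, P(≥1) = 0.5695, P(≥2) = 0.1869 and P(≥3) = 0.0381. The chance is p² × 0.5695 + 2p(1 − p) × 0.1869 + (1 − p)² × 0.0381.
- p = 0.28: 0.0447 + 0.0754 + 0.0197 = 0.140.
- p = 0.55: 0.17228 + 0.09251 + 0.00771 = 0.2725 (0.27251 unrounded), or 27.3%.

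**Step 5. Bounds and a milder case.** If radiation response were certain (p = 1), steps 3 and 4 give 22.5% and 57.0%. If affected lesions respond with chance q alone (p = q), the ranges are 8.7–13.9% with one patient and 10.7–24.5% with two.

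| Affected patients | Milder, p = q | Independent effects | Certain response |
|---|---|---|---|
| 0 | 7.0% | 7.0% | 7.0% |
| 1 | 8.7–13.9% | 10.1–14.8% | 22.5% |
| 2 | 10.7–24.5% | 14.0–27.3% | 57.0% |

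**Step 6. Properties of an ORR restricted to out-of-field lesions.** A subject with no out-of-field injected lesion is scored a non-responder, so 3 responses must come from the rest.
- One such subject: power P(≥3 of 9 at 40%) = 1 − 0.0101 − 0.0605 − 0.1612 = 76.8%; alpha 5.3%.
- Two such subjects: power P(≥3 of 8 at 40%) = 1 − 0.0168 − 0.0896 − 0.2090 = 68.5%; alpha 3.8%.

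**The case against.** The strongest reply is that lesion selection is already governed by RECIST 1.1. The SAP defers target selection to it and allows only target tumors to be injected. If RECIST 1.1 limits the use of irradiated lesions, the gap may be partly closed. Its text is not in the documents, and neither is the protocol clarification letter of 08MAR2023 on which the SAP also relies. This reply stands as a limit on confidence. It does not close the point: neither document states a radiation condition, and Protocol Section 4.2 covers all accessible measurable tumors, which is wider than the SAP.

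The second reply is that safety is the primary endpoint, every efficacy endpoint is secondary, and SAP Section 3.3 disclaims formal efficacy hypotheses. That lowers the weight of the point. The same section nevertheless attaches a criterion for further study to ORR.

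The third reply is that such patients may be few, and that inclusion 5 restricts entry with non-injectable disease. Both are fair. With 10 evaluable subjects, though, one response is 10 percentage points.

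A reader might also infer that the SAP positively requires irradiated lesions to count, because it says "Injected tumors will not be assessed per RECIST v1.1 but solely per the criteria" set out in the protocol. That sentence fixes the definitions of CR, PR, SD and PD. It does not decide which lesions are selected.

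**Conclusion.** The gap is real as a matter of wording: followed as written, the plan can count radiation shrinkage as an injected-tumor response. Confidence is moderate, because a source outside the documents may restrict target selection. The sample-size figures themselves are correct.

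Under the independence assumption, the chance of meeting the 3-of-10 criterion at a true ORR of 10% roughly doubles at most with one affected patient (7.0% to 14.8%) and roughly quadruples at most with two (7.0% to 27.3%). At the low end of the milder assumption, one patient leaves it at 8.7%, still under the 10% target.

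A reader might take 22.5% and 57.0% as the expected size. They are upper bounds that need certain radiation response, which nothing in the documents supports.

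A reader might also conclude that in-field lesions should be struck from the RECIST target set. Under the SAP, non-target tumors are not to be treated, so that step would change who receives injections. It is a clinical decision and no part of this point.

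**What to change.** Change the analysis only. Enrolment, target selection and injection stay as they are.

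1. For each injected lesion, record the date and field of any radiation given less than 4 weeks before first injection, and flag in-field lesions in the response listing.
2. Add to SAP Section 6.2.2.1 a prespecified injected-tumor ORR that uses only injected lesions outside that field. Subjects with none count as non-responders, and the denominator remains the efficacy evaluable population.
3. Report it beside the main ORR. Describe the 3-of-10 criterion as met without qualification only if it also holds in this analysis.
4. Reconcile Protocol Section 4.2 with SAP Section 3.1 and the Injected Tumor Response Criteria Details on which tumors are treated. If the sponsor relies on RECIST 1.1 to limit irradiated lesions, say so explicitly.

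**Cost.** Some extra lesion-level data: the documents show radiation history taken at baseline, but no date or field by lesion. Power in the added analysis falls to 76.8% with one subject who has only in-field injected lesions and to 68.5% with two, against the stated 83%. A true drug response in a recently irradiated lesion would not count there, though it still counts in the main ORR.

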3.3 Informed Consent Process

All participants must be provided a consent form describing the study with sufficient information for participants to make an informed decision regarding their participation. Participants must sign the Institutional Review Board (IRB) approved informed consent prior to participation in any study specific procedure. The participant must receive a copy of the signed and dated consent document. The original signed copy or certified copy of the consent document must be retained in the medical record and research file. This signed consent form present in the medical record shall be considered documentation that the GCP informed consent process has been completed.

3.4 Subject Withdrawal

While subjects are encouraged to complete all study evaluations, they may withdraw from the study at any time and for any reason. Subjects receiving chemotherapy (other than F-araAMP) or radiation therapy will be removed from the study. Participation is voluntary, and declining to participate will involve no penalty, or loss of benefits to which the participant is otherwise entitled. The subject will be encouraged to maintain contact with the investigator and report any serious AEs experienced for the entire study period. Individuals who withdraw early from treatment will be asked to complete Day 56 (of the last treatment cycle) study visit evaluations.

Subjects who withdraw or complete the study are not eligible to re-enter or be treated in the study again. Subjects who drop out following administration of study agent will not be replaced.

Screen failures will include participants who consented and entered into the screening process appropriately, but subsequently did not meet the entry criteria and did not receive study drug. The investigator will maintain a screening log that documents the subject number, subject initials, and reason(s) for screen failure. No data other than reason for screen failure and basic screening data will be collected on Screen Failures. Participants who fail screening will not be followed for safety or activity of study drug, and no other study procedures will be performed. Screen failures will be replaced.

4. TREATMENT PLAN

4.1 Dose and Dose Rationale

The dose selected for evaluation with repeat administration has been chosen based upon tumor response and safety of the vector (Ad/PNP) and prodrug (F-araAMP) seen with single administration of this dose level in the completed Phase 1 study. With each cycle the subject will receive a total dose of 6×10^{11} VP Ad/PNP followed by a total dose of 75 mg/m^2 F-araAMP.

4.2 Administration of Ad/PNP-F-araAMP per Cycle

With each cycle, subjects will receive 3 intratumoral administrations of 2.0×10^{11} VP Ad/PNP over 2 days followed by 3 daily infusions of 25 mg/m^2 F-araAMP in the outpatient clinic or in-hospital at the discretion of the investigator. The physician or a designee trained to do the injections by the Principal Investigator (PI) will administer intratumoral Ad/PNP during each cycle. The outpatient unit is staffed with medical personnel to treat emergency and non-emergency medical events.

Ad/PNP will be given via direct intratumoral injection three times over 2 days. If needed, the investigator may utilize radiologic guidance (e.g., ultrasound) to assist in the injection of Ad/PNP. Two intratumoral administrations will be given on Day 1 and one intratumoral administration on Day 2. The first administration will occur on the morning of Day 1 and the subject monitored closely for 1 hour for acute injection-related events. Approximately 3-6 hours after the first administration, the subject will receive the second intratumoral administration on Day 1. The third intratumoral administration will be given on the morning of Day 2.

Vials of Ad/PNP will be thawed and prepared for injection by the investigational pharmacy according to the Preparation of Investigational Product Instructions. In the Phase 1 study, Ad/PNP was administered intratumorally in a 0.5 ml volume ($\sim 2 \times 10^{11}$ VP/ml or $\sim 2 \times 10^{12}$ VP/ml); both dose levels showed activity and were well tolerated. In the Phase 1/2 study, 2×10^{11} VP will be administered in volumes up to 5 ml (4×10^{10} VP/ml) so that vector can be dispersed more effectively throughout needle-assessable tumor tissue.

The volume of vector injected into each tumor will be according to tumor volume. All measurable tumors that are accessible for intratumoral injection will be identified and treated for each enrolled subject

Subjects will receive a total of 2×10^{11} VP Ad/PNP per injection (3 injections per cycle) distributed across the injected tumors and volume of vector will vary dependent upon estimated tumor volume using the tumor's two dimensions measured by calipers as described in the Operating Procedure - Injection of Investigational Product into the Tumors of Human Subjects. For example, for a subject with 3 tumors of 1.5 ml, 3 ml, and 5 ml size each, 2×10^{11} VP Ad/PNP will be suspended in 3.5 mL and tumors injected with 0.5 mL, 1.0 mL, and 2.0 mL, respectively. If the tumor mass is very large or the total volume for all discreet tumors exceeds 16 ml, a portion of the tumor mass or certain discrete tumors will be selected by the physician and injected with 5 ml of Ad/PNP. The same tumors will be injected with each administration of 5 ml Ad/PNP.

Lesion Volume	Injection Volume
> 16 ml	5.0 mL
12 ml to 16 ml	4.0 mL
8 ml to 12 ml	3.0 mL
4 ml to 8 ml	2.0 mL
2 ml to 4 ml	1.0 mL
Less than 2 ml	0.5 ml

Using aseptic technique, the Ad/PNP solution will be injected percutaneously with injection at multiple sites within the tumor to achieve thorough infiltration. A subcutaneous injection of local anesthetic may be used, if desired.

Approximately 24 to 36 hours following the third administration of Ad/PNP into the tumor (Day 3), subjects will receive 25 mg/m^2 F-araAMP daily for 3 days. F-araAMP will be prepared and administered intravenously over approximately 30 minutes per the package insert. Subjects who do not receive all three administrations of Ad/PNP will not receive F-araAMP; all subjects will be assessed for safety at the scheduled study visits. Subjects who do not receive all three full doses of Ad/PNP may be eligible to receive subsequent doses of F-araAMP at the discretion of the investigator.

In this study, each 5-day course of treatment will commence every 28 days +/- 3 days and subjects will receive up to 5 cycles of Ad/PNP-F-araAMP. The 28-day interval complies with the recommended dosing schedule between courses of F-araAMP used to treat hematological malignancies. Treatment will be discontinued prior to 5 cycles in the event of injected tumor progression (and/or the investigator determines the patient may no longer stand to benefit from further

treatment) or if there is no tumor present for injection. In the event that treatment is discontinued, the subject should complete the Day 28 and Day 56 visits of the last treatment cycle.

Subjects will be monitored for clinical safety events and changes in laboratory parameters throughout the study period. Subjects who experience a CR before the next cycle will not receive treatment but will continue to be followed during the study period. Subjects whose tumors achieve a CR but then recur during the study period may resume treatment with Ad/PNP-F-araAMP up to the maximum allowed 5 total cycles.

No formal follow-up visits are planned following the end of the study period (Day 56 of the last treatment cycle). However, the Investigational New Drug (IND) Sponsor may request follow-up information from the investigator on tumor status in subjects who have stable disease (SD), PR, or CR at completion of their study participation.

